3.3. Study Endpoints

3.3.1. Definitions

Acute Limb Ischemia[55]: Defined by the operating or treating physician. Typically defined as emergently threatened, whether marginally or immediately, implying reversible ischemia in a limb that is salvageable without a major amputation if arterial obstruction is relieved quickly or irreversible ischemic change requiring major amputation.

Adverse Event (AE): Any untoward medical occurrences, unintended disease or injury or any untoward clinical signs (including abnormal laboratory findings) in patients, users or other persons related to the investigational medical device or procedure.[56] For this study, only device or procedure related AEs need to be reported.

Device Fracture: A stent fracture was defined as any discontinuity of the normal structure of the stent as diagnosed on x-ray.

Endoleak (Modified from White et al.)[57]:

Type I – Present when a persistent perigraft channel of blood flow develops due to inadequate or ineffective seal at the graft ends.

Type II – Occurs when there is persistent collateral blood flow into the aneurysm sac flowing retrogradely from collateral branches.

Type III – Arises at the mid-graft region due to leakage through a defect in the graft fabric or between the segments of multiple grafts.

Type IV –Blood diffusion across the pores of the graft fabric or through tiny holes in the graft fabric caused by sutures or stent struts.

Type V - Leakage from an unknown origin.

Hinge Point: Located at the adductor tubercle, which corresponds to the upper border of the patella, in a plane perpendicular to the femoral axis.

Length of Hospital Stay: The number of days the subject remains in the hospital due to endovascular repair of a PAA with VIABAHN (“index procedure”).

Length of Procedure: The number of minutes the subject remains in the operating room or catheterization laboratory due to endovascular repair of a PAA. If no specific information is available the first and last angiographic timestamp can be used to capture the length of the procedure.

Limb Loss: An amputation on the study limb above the metatarsals.

Migration: Any post-operative device migration requiring treatment.

Patency:

Primary Patency: Blood flow without occlusion maintained through the device after implant without an intervention.

Primary Assisted Patency: Blood flow maintained through the device after implant regardless of re-interventions performed (without occlusion).

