5.7. Follow-Up

Follow-up visits need to be done in a window of +/- 90 days in order to be documented as study visits. This means that 12 month follow-up visit needs to take place between 275 and 455 days post-procedure, the 24 months follow-up visit between 640 and 820 days post-procedure, and the 36 month follow-up visit between 1005 and 1185 days post-procedure. All visits occurring from the time of procedure through 1185 days post-procedure should be recorded for each subject. If a subject had an office visit between 1005-1185 (three years \pm 90) days post-procedure, then no further information will be collected on the subject after 1185 days. Device or procedure related AEs, antiplatelet / anticoagulant medications, clinical assessment, ultrasound, and angiographic information should be collected, during each follow-up visit as applicable and available.

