5.9. Subject Study Completion

A subject has completed the study when 36 months (1185 days or 3x365 + 90 days) of follow-up data has been recorded on the CRFs. Any subject that does not complete these requirements due to voluntary withdrawal, death, lost secondary patency (e.g. had a study limb bypass) or any other reason will be considered a withdrawal and the reason for discontinuation will be marked on the CRF.

If a subject is lost to follow-up, the appropriate CRF must be completed as soon as possible after subject status has been determined. If a subject fails to comply with follow-up evaluations, the Site must make at least three attempts to contact the patient and his family and potentially his General Practitioner. Each attempt to contact the subject and the method used (e.g., telephone contact, registered letter) must be documented in the subject's records.

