8.4. Risk-to-Benefit Rationale

CONFIDENTIAL INFORMATION

MD133246 Protocol Template
Revision#: 1
Doc Type: GC

This study does not lead to any change in patient management and patients will receive the same treatment as they would have received if they had decided not to participate. Therefore, there is neither an additional risk nor a direct benefit related to the participation in the study.

9. Adverse Events and Safety Monitoring

AEs are defined as any untoward medical occurrences, unintended disease or injury or any untoward clinical signs (including abnormal laboratory findings) in patients, users or other persons whether or not related to the investigational medical device.[56] According to the primary and secondary endpoints of this study, the documentation of adverse events will concern all serious adverse events and adverse events related to the initial study procedure or the study device, regardless of the severity throughout 36 months.

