9.1.3. Adverse Event Reporting and Coding

AEs will be reported on the appropriate CRF for that visit and documented in the subject's permanent medical record. The Investigator at each Site is ultimately responsible for reporting AEs to the Sponsor. The Investigator shall supply the Sponsor with any additional requested information.

Timely and complete reporting of safety information assists the Sponsor in identifying any untoward medical occurrence, thereby allowing: (1) protection of safety of study patients; (2) a greater understanding of the overall safety profile of the GORE® VIABAHN® Endoprosthesis; (3) appropriate modification of study protocols; and (4) adherence to worldwide regulatory requirements.

The following information should be collected for each reported AE:

- AE Name
- AE Onset Date
- Relationship
- Classification (serious / non-serious)
- Treatment
- Outcome
- Resolution Date

All reported AEs will be coded using the Medical Dictionary for Regulatory Activities (MedDRA).

In reporting AEs the following submission guidelines should be followed:

- AE reporting begins once the subject has received a GORE® VIABAHN® Endoprosthesis and continues until study completion / discontinuation.
 - NOTE: Any AE that occurs while the subject is in the operating room / catheterization laboratory should not be recorded as an AE, unless it is unresolved when the subject leaves the operating room / catheterization laboratory.
 - NOTE: Any AE occurring after the final study visit will not be recorded in this study.
- AEs with an outcome status of "Ongoing" should be assessed at each follow-up evaluation to determine if the event has resolved. AEs ongoing at study completion / discontinuation should be left as "Ongoing" on the AE CRF.

CONFIDENTIAL INFORMATION

MD133246 Protocol Template

Revision#: 1

Doc Type: GC

- Clinical sequelae present at baseline should be recorded on the Medical History CRF. If the clinical sequela increases in severity or frequency from baseline then it should be reported as an AE.
- If known, the diagnosis of the underlying illness or disorder should be recorded, rather than its individual symptoms. If unable to provide a diagnosis, report the symptoms as separate events. AEs should be reported using the full name without abbreviations or narratives.

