- Subject Completion/Discontinuation (Completion/Discontinuation [Surgical bypass, Amputation above the metatarsal, Lost to follow-up, Death, Other])
- Repeat Interventions Summary (Days to First Intervention, Reason for Reintervention, Endoleak at Time of Intervention [Endoleak, Type], Type of Reintervention Performed, Successful Reintervention, ABI at Discharge)

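### The plan does not say whether data collection continues after a study-limb bypass or amputation, so later limb loss, SAEs and deaths may go unrecorded at some sites

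*Protocol*

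**What the plan says.** Some of the text points towards stopping:

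- Protocol 5.9 opens its withdrawal rule with "Any subject that does not complete these requirements due to", then lists causes that include voluntary withdrawal, death and "lost secondary patency (e.g. had a study limb bypass) or any other reason will be considered a withdrawal and the reason for discontinuation".
- Protocol 9.1.3 says that AE reporting "continues until study completion / discontinuation". Its note adds: "Any AE occurring after the final study visit will not be recorded in this study".
- The completion/discontinuation table in SAP 8.1 has the categories "Surgical bypass, Amputation above the metatarsal, Lost to follow-up, Death, Other".

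Other text points towards continuing:

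- Protocol 5.7: "All visits occurring from the time of procedure through 1185 days post-procedure should be recorded for each subject".
- Protocol section 9 asks for all SAEs and for "adverse events related to the initial study procedure or the study device, regardless of the severity throughout 36 months".
- Protocol 5.8 names neither bypass nor amputation among its reasons for termination.
- Protocol 3.2 has patients followed through 24 and 36 months, and 5.12 has each subject followed for about 36 months before exit.

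Limb loss is defined on the limb, not on the device: "An amputation on the study limb above the metatarsals" (Protocol 3.3.1). SAP 2.3.2.2 and 5.5 estimate freedom from limb loss by time-to-event analysis at 12, 24 and 36 months.

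**The concern.** Neither document says whether limb status, SAEs or vital status are collected after a bypass or an amputation. Two sites could each follow the text faithfully and collect different data.

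Where a site stops at bypass, the limb-loss Kaplan-Meier curve must censor that patient because treatment of the same limb failed. Such censoring is uninformative only if limb-loss risk after bypass equals the risk in patients still followed. If the risk after bypass is higher, the curve flatters the device. If no limb is lost after bypass, the error is slightly in the other direction. No censoring rule for this endpoint is visible in the SAP.

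The 24- and 36-month SAE counts and the listing of deaths (SAP 8.2) would also be cut short. After a study-limb amputation above the metatarsals the limb-loss event is already counted, so only later SAEs and deaths are exposed. Secondary patency is not exposed to a stop at bypass, because bypass is itself a failure of that endpoint.

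**Working it through.** **Reading the text.** Protocol 5.9 is conditional. It classifies a subject who does not complete; it does not order exit at bypass. But it accepts bypass as a cause of non-completion, the SAP provides a category for it, and 9.1.3 ends AE reporting once discontinuation is recorded. Amputation appears as an exit reason only in the SAP. The day-1185 figure is consistent throughout (3 × 365 + 90 = 1185), so 5.7 and 5.9 describe the same follow-up period and differ only on who must reach its end.

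**Who is exposed.** Inclusion is retrospective (Protocol 3.2), and Table 4 places enrolment with the 12-month visit. Bypasses before enrolment are much less affected, because later events may already be in the chart. The model below therefore treats only bypasses after enrolment month *s* as unobserved.

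**Inputs.** There are 50 patients (Protocol 3.2). The documents give no rate for bypass or for limb loss with this device, so these are assumptions:

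- 36-month bypass risk *b* = 5% or 20%
- limb loss without bypass *r* = 1% or 2%
- limb loss after bypass *a* = 10% or 30%

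The only related figure in the documents is limb salvage of 75–100% after surgical repair (Protocol 1.2). It implies *a* = 0–25% but is not specific to bypass after device failure.

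**Model.** Hazards are constant: λb = −ln(1−b)/36, λr = −ln(1−r)/36, λa = −ln(1−a)/36 per month. Write k = λb + λr.

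- True 36-month freedom from limb loss: e^(−36k) + λb·[e^(−36λa) − e^(−36k)]/(k − λa)
- Patients bypassed after month *s*: 50·(λb/k)·[e^(−ks) − e^(−36k)]
- Understatement: true limb loss minus the Kaplan-Meier value when bypasses after *s* are censored

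**Worked corner** (b = 20%, r = 1%, a = 30%). λb = 0.00620, λr = 0.00028, λa = 0.00991, k = 0.00648.

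- True freedom = 0.792 + 0.00620 × (0.700 − 0.792)/(0.00648 − 0.00991) = 0.958, so true limb loss is 4.17%.
- With every bypass censored (s = 0), Kaplan-Meier gives 1.00%, a difference of 3.17 points.
- With s = 12 it gives 2.88%, a difference of 1.30 points.
- Patients bypassed after month 12: 50 × 0.957 × (0.925 − 0.792) = 6.4.

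**All corners** (understatement of 36-month limb loss in percentage points):

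| Enrolment month | Bypassed later, per 50 | a = 10–30% | Missed amputations per 50, a = 10–30% | a = 0–25% |
|---|---|---|---|---|
| 12 | 1.6–6.4 | 0.09 to 1.30 | 0.06–0.72 | −0.08 to 1.05 |
| 18 | 1.2–4.7 | 0.05 to 0.70 | 0.03–0.40 | −0.04 to 0.57 |
| 29.5 | 0.4–1.6 | 0.01 to 0.09 | 0.004–0.05 | −0.005 to 0.07 |

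Month 29.5 is a patient implanted on 15 September 2012 and enrolled on 1 March 2015: 897 days, with (1185 − 897)/1185 = 24% of follow-up still ahead. When a = r the bias is zero at every *s*. Censoring every bypass, including those before enrolment, is an upper case: 0.2 to 3.2 points for a = 10–30%.

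**Primary 12-month safety count.** Even if all 50 enrolled at day 275, the start of the 12-month window, only 0.2 (b = 5%) to 0.9 (b = 20%) patients would have a bypass between then and month 12.

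**The case against.** No sentence tells a site to stop at bypass or amputation. The SAP entry is a row in a disposition table, and several sections besides 5.7 and 9 assume follow-up to 36 months. The protocol summary even lists bypass surgeries among the data to be collected. This is right, and it is why the finding is one of ambiguity and not of a wrong rule. It does not settle what a site does after recording bypass as the reason for discontinuation.

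The month-12 figures describe a cohort unlike the one planned. Screening is consecutive from 15 September 2012 and enrolment was expected from March to December 2015, so by 31 December 2015 the earliest patients would be at day 1202, past the end of follow-up. Spreading implants evenly from the start date to 12 months before consent, the same assumed rates with a = 10–30% give about 0.03 to 0.57 points. One patient in 50 is 2 points, and the binomial standard error at 98% is √(0.98 × 0.02/50) = 2.0 points. This stands: month 12 is an upper case, and the likely bias is small beside sampling error.

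The rates are assumed, and the 75–100% limb salvage carries no time horizon of its own. This stands too. Dataset and output specifications are separate documents and may hold a censoring rule, so the statement about censoring is limited to the visible SAP. Finally, records after exit may lie with another physician (Protocol 5.8), so some will be harder to obtain.

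**Conclusion.** The concern holds. Protocol 5.9 and 9.1.3 and SAP 8.1 cannot be reconciled with Protocol 5.7 and section 9 without a further rule, and sites may differ. That conclusion rests on the text alone and is firm.

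The size and direction of any bias are not firm. Under the assumed rates the understatement of 36-month limb loss runs from close to zero to 1.3 points. It depends mostly on how far into follow-up patients are at enrolment, and every range includes zero if limb loss after bypass is 0–25%. The number of SAEs and deaths that would go unrecorded was not estimated. The primary 12-month safety count is barely touched, and the primary patency result is not called into question. It should be fixed because it affects the long-term safety results the study exists to document and is cheap to remove.

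**What to change.** - **Protocol 5.9 and 9.1.3:** state that a bypass, loss of secondary patency or study-limb amputation counts as an endpoint event where it meets that endpoint's definition, but does not end data collection. Limb status (after bypass), SAEs, related AEs and death continue to be recorded from standard-of-care records to day 1185, unless the patient withdraws consent, dies or is lost to follow-up.
- **SAP 8.1:** bring the discontinuation categories into line with this.
- **SAP 5.5:** state that limb loss is not censored at bypass and that SAE counts are not truncated at bypass or amputation.
- **Reporting:** give the number of patients without post-bypass data, with a limb-loss sensitivity analysis that counts them all as limb loss and then all as no limb loss. With 6.4 such patients the two bounds would be about 13 points apart (6.4/50). They show how much is unknown and are not estimates.

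The cost is protocol and SAP wording, submission of the amendment to CCTIRS and CNIL with site training (Protocol 6.5), a few more CRF pages, and some effort to obtain records held elsewhere. No visit, test or treatment is added. The limb-loss and SAE figures may come out slightly less favourable.

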5.10. Device Deficiencies

Device deficiencies are defined as inadequacy of a medical device with respect to its identity, quality, durability, reliability, safety or performance. The process for reporting device deficiencies should be done through normal product surveillance mechanisms.

5.11. Explant Procedures

The GORE® VIABAHN® Endoprosthesis may be explanted during a surgical procedure or as part of an autopsy. If the explanted study device is available, Sites are requested to return the explanted device to the Sponsor for gross and histological evaluation. Contact the Gore Associate managing the study to facilitate shipment of a specimen shipping kit. The specimen

CONFIDENTIAL INFORMATION

kit provides specific packaging and handling instructions for the specimen and contains a shipping container.

5.12. Duration of Investigation

Each subject will be followed for approximately 36 months and then exit the investigation. It is anticipated that all patients will be enrolled within a period of nine months. The subject enrolment period is expected to occur from March 2015 to December 2015. The last subject primary endpoint follow-up is expected to occur by the end of 2017.

6. Study Administration

6.1. Training

Each physician deploying the GORE® VIABAHN® Endoprosthesis has extensive experience with this commercially available device and study Sites will be selected accordingly. No additional training for this product will be required.

6.2. Monitoring

[REDACTED]

The monitors are qualified by training and experience to oversee the progress of the study at the Site and will ensure that the Investigators and their staff understand and adhere to both the applicable regulatory requirements and the study protocol. In addition, they may assist in resolution of any problems that may arise during the study. A monitoring plan will be developed prior to the initiation of the Post-market study which outlines the extent and nature of monitoring appropriate for the study, including the frequency of visits, the strategy for source data verification, based on considerations such as the objective, design, complexity, size, critical data points, and endpoints of the study.

6.2.1. Site Initiation

Site initiation will be performed to assure that each Investigator and his / her staff understands the protocol, applicable regulations, human subject protection requirements and the Investigator's obligations. This visit will ensure that required documentation with the appropriate approval is in place prior to subject enrollment.

6.2.2. Periodic Site Monitoring

Periodic Site monitoring will occur as necessary to ensure continuing adequacy of facilities and adherence to the clinical study protocol, Good Clinical Practice (GCP), ISO 14155 and applicable regulations, and laws that pertain to the conduct of the clinical study.

All data will be verified to source during the monitoring process, other than instrument data directly downloaded into the investigational database [REDACTED]

[REDACTED] will be responsible for monitoring this Post-market study.

The monitoring plan will specify Site audits and inspections as indicated by the Sponsor. Regulatory authorities will have the ability to inspect and audit the investigational Site during the clinical study.

6.3. Device Accountability and Storage

The GORE® VIABAHN® Endoprosthesis is a commercially available product and has already been used, so accountability or storage for this study is not required. The lot and serial number for each commercial device used in the study will be recorded in the subject records and transcribed to the CRF.

6.4. Protocol Deviations

A protocol deviation is defined as any change, divergence or departure from the study design or procedures of a research protocol that is under the Investigator's control. The Investigator is responsible for promptly reporting protocol deviations to the Sponsor. The Sponsor will determine the effect of the protocol deviation on the scientific soundness of the clinical study and subject safety, and determine if additional reports or actions are required. Additional action may include Site retraining and / or Site termination.

6.5. Protocol Amendments

The Sponsor will obtain CCTIRS and CNIL approval before starting collecting the data; on all amendments will also be submitted in a timely manner to the CCTIRS and to CNIL. The Sponsor will ensure proper training of Investigator and Site staff on all protocol amendments.

6.6. Access to Source Data / Documents

Source data are defined as all information necessary for the reconstruction and evaluation of the clinical investigation. The Investigator will keep all study records and source data available for inspection by the Sponsor, MedPass monitors, CCTIRS, CNIL, and other regulatory authorities.

6.7. Study Records Retention

All data shall be produced and maintained in a way that assures control and traceability. Source documents are required for each subject enrolled. The Investigator will maintain complete, accurate and current study records as required by applicable regulatory requirements. Records will be maintained during the clinical study and for a minimum of 15 years after the latter of the date on which the study is terminated or completed, or the date the records are no longer required to support regulatory approval of the device. In any event, clinical study records will not be disposed of, nor custody of the records transferred, without prior written Sponsor approval. Where copies of the original source document as well as printouts of original electronic source documents are retained, these shall be signed and dated by a member of the investigational Site team with a statement that it is a true reproduction of the original source document.

Investigator records will include, but not be limited to:

- All correspondence with another Investigator, CCTIRS, CNIL, the Sponsor, a monitor, including required reports.
- Records of each subject's case history and exposure to the device. Case histories include the CRFs and supporting data, medical records, including, for example, progress notes of the physician, the individual's hospital chart(s), and the nurses' notes. Such records shall include:
 - All relevant observations, including records concerning AEs, the information, date and condition of each subject upon entering the trial, information about relevant previous medical history, and the results of all diagnostic tests.

CONFIDENTIAL INFORMATION

- A record of the exposure of each subject to the device, including the date and time of implant, and any other therapy.
- The protocol, any amendments and documentation of any deviations from the protocol, including the dates, and the reasons for such deviations.
- Any other records that are required to be maintained by regulation or by specific requirement for a category of investigations or a particular investigation.

The Investigator will prepare and submit the following reports:

- **Protocol Deviations:** Protocol Deviations shall be reported as described in Section 6.4
- **Other:** Any other reports as reasonably requested by the Sponsor.

[figure not shown]
